13.1 Data and output handling

To ensure reproducibility and to keep an audit trail, all data management, analysis and outputting procedures will be kept as Stata **do** files. All transformation, categorisation, or creation of variables as well as keeping or dropping of subjects in specific analyses will be written in the do files. The **do** files are to be executed in order to obtain these new data features temporarily, as opposed to saving these new features into permanent data files. It is envisaged that a large number of commands are required, and they may need to be partitioned in more than one **do** file. Numeric values will be used to indicate the correct sequence for running these files and version number of the do file is indicated at the file name, e.g. iLiNS-DOSE data cleaning01, form 18, v01.0, 2012-12-27. If data from more than one form are used the form number is not indicated in the do-file name but forms are listed in the comments section in the beginning of the do-file. Variables on data version and version date are included in the data file and people using the data are asked not to share the files with other approved data users. All approved users obtain the data from the data manager so that the latest version is distributed. Outputs will be saved as log files.

A master **do** file, for example, may include, but is not limited to, the following commands to execute all the data modification, analyses and outputting procedures in one go:

**** Example of a master do file

**** DOSE main paper, master do file
clear
version 11.2
set more off
set mem 50m
cd c:\dose\mainpaper
capture log close
log using mainpaper.log, text replace
do iLiNS-DOSE data cleaning01, form 18, v01.0, 2012-12-27.do
do iLiNS-DOSE data analysis02, form 18, v01.0, 2012-12-27.do
do iLiNS-DOSE data analysis03, form 18, v01.0, 2012-12-27.do
log close

14 Procedures and history on modifications to the analysis plan

All new versions of and additions to the statistical plan will be approved by a team of core investigators, consisting of the senior researchers who oversee the trial implementation (iLiNS-Malawi Board of Directors) and the study statisticians. Each version will be identified with a new version number and a date of approval and named with standardized file-name format (iLiNS-DOSE analysis plan, version 00.3, 2012-12-27.docx).

In the file name, the first two digits before the decimal indicate an approved change to the SAP (ie version 01.0 denotes the first approved version, 03.0 the third approved version etc). The last digit after the decimal indicates a yet unapproved revision number for a document under editions (eg. 02.1 points to a document that is based on the second approved version, but has undergone one round of yet unapproved editions to it).

The table below lists the editions made to the different approved versions of the SAP:

Version number	Date of approval	Editions
01.0	xx.xx.2013	Original document

15 References

Nauta J. Statistics in Clinical Vaccine Trials. Heidelberg. Springer. 2010.

Senn S. Statistical Issues in Drug Development. Chichester, GBR. John Wiley & Sons. 1997.

16 Appendixes

Statistical Analysis Plan, Appendix 1: Secondary growth outcomes

Statistical Analysis Plan, Appendix 2: Developmental outcomes at age 18 months (added on 07.05.2013).

Statistical Analysis Plan, Appendix 3: Breast milk intakes (added on 07.05.2013).

Statistical Analysis Plan, Appendix 4: The effect of LNS on physical activity (added on 24.05.2013).

Statistical Analysis Plan, Appendix 5: Effect on infant and young child feeding practices (added on 26.07.2013, revised into version 02 on 28.04.2014).

Statistical Analysis Plan, Appendix 6: Hypothetical Willingness-to-Pay for LNS and Likuni Phala at Baseline (added on 25.04.2014).

Statistical Analysis Plan, Appendix 7: Long-term acceptability of LNS (lipid-based nutrient supplements) for infants in Malawi (added on 28.05.2014)

Statistical Analysis Plan, Appendix 8: The effect of Lipid-based Nutrient Supplement (LNS) provision on child morbidity (added on 28.05.2014)

17 Legends to the figures

- Figure 1. Participant flow in CONSORT recommended format (Lancet 2001: 357: 1193)
- Figure 2. Box-Whisker plots of change in LAZ by groups
- Figure 3. Cumulative incidence curve for mortality, by intervention groups

18 Figures

Figure 1. Participant flow

Figure 2. Box-Whisker plots of change in LAZ by groups

19 Tables

Table 1a Baseline characteristics of participants at enrolment

Variable	Control	10g milk	20g milk	20g milk-	40g milk	40g milk-	Test
		LNS	LNS	free LNS	LNS	free LNS	
Number of participants	XXX	XXX	XXX	XXX	XXX	XXX	
Age, months (mean, SD, N)	xx.x (xx.x)	xx.x (xx.x)	xx.x (xx.x)	xx.x (xx.x)	xx.x (xx.x)	xx.x (xx.x)	ANOVA
Proportion of Males (percentage)	xxx / xxx (xx%)	xxx/ xxx (xx%)	Chi-squared				
Weight, kg (mean, SD, N)	xx.x (xx.x)	xx.x (xx.x)	xx.x (xx.x)	xx.x (xx.x)	xx.x (xx.x)	xx.x (xx.x)	ANOVA
Length, cm (mean, SD, N)	xx.x (xx.x)	xx.x (xx.x)	xx.x (xx.x)	xx.x (xx.x)	xx.x (xx.x)	xx.x (xx.x)	ANOVA
Middle upper arm circumference, cm (mean, SD, N)	xx.x (xx.x)	XX.X (XX.X)	XX.X (XX.X)	xx.x (xx.x)	xx.x (xx.x)	xx.x (xx.x)	ANOVA
Head circumference, cm (mean, SD, N)	xx.x (xx.x)	xx.x (xx.x)	XX.X (XX.X)	xx.x (xx.x)	XX.X (XX.X)	xx.x (xx.x)	ANOVA
Weight-for-age z-score (mean, SD, N)	xx.xx (xx.xx)	XX.XX (XX.XX)	XX.XX (XX.XX)	xx.xx (xx.xx)	xx.xx (xx.xx)	xx.xx (xx.xx)	ANOVA
Length-for-age z-score (mean, SD, N)	xx.xx (xx.xx)	XX.XX (XX.XX)	XX.XX (XX.XX)	xx.xx (xx.xx)	xx.xx (xx.xx)	xx.xx (xx.xx)	ANOVA
Weight-for-length z-score (mean,	xx.xx (xx.xx)	XX.XX (XX.XX)	XX.XX (XX.XX)	xx.xx (xx.xx)	xx.xx (xx.xx)	xx.xx (xx.xx)	ANOVA

SD, N)							
MUAC z-score (mean, SD, N)	XX.XX (XX.XX)	XX.XX (XX.XX)	xx.xx (xx.xx)	xx.xx (xx.xx)	xx.xx (xx.xx)	xx.xx (xx.xx)	ANOVA
Head circumference z-score (mean, SD, N)	xx.xx (xx.xx)	xx.xx (xx.xx)	xx.xx (xx.xx)	xx.xx (xx.xx)	xx.xx (xx.xx)	xx.xx (xx.xx)	ANOVA
Incidence of severe stunting at 6	xxx / xxx	xxx/ xxx	xxx/ xxx	xxx/ xxx	xxx/ xxx	xxx/ xxx	Fisher's
months of age (percentage)	(xx%)	(xx%)	(xx%)	(xx%)	(xx%)	(xx%)	exact test
Incidence of moderate and severe	xxx / xxx	xxx/ xxx	xxx/ xxx	xxx/ xxx	xxx/ xxx	xxx/ xxx	Fisher's
stunting at 6 months of age	(xx%)	(xx%)	(xx%)	(xx %)	(xx%)	(xx %)	exact test
(percentage)							
Blood hemoglobin concentration	xx.x (xx.x)	xx.x (xx.x)	xx.x (xx.x)	xx.x (xx.x)	xx.x (xx.x)	xx.x (xx.x)	ANOVA
g/dl (mean, SD, N)							
Proportion of participants with	xxx / xxx	xxx/ xxx	xxx/ xxx	xxx/ xxx	xxx/ xxx	xxx/ xxx	Chi-squared
anaemia (percentage)	(xx%)	(xx%)	(xx%)	(xx%)	(xx%)	(xx%)	
ZPP concentration $\mu g/g$ (mean, SD,	xx.x (xx.x)	xx.x (xx.x)	xx.x (xx.x)	xx.x (xx.x)	xx.x (xx.x)	xx.x (xx.x)	ANOVA
N)							
ZPP concentration >45 (percentage)	xxx / xxx	xxx/ xxx	xxx/ xxx	xxx/ xxx	xxx/ xxx	xxx/ xxx	Chi-squared
	(xx%)	(xx%)	(xx%)	(xx%)	(xx%)	(xx%)	

Table 1b Other baseline characteristics to be assessed

Variable	Control	10g milk LNS	20g milk	20g milk-free	40g milk	40g milk-	Test
			LNS	LNS	LNS	free LNS	
Maternal Age, years (mean, SD, N)	xx.x (xx.x)	xx.x (xx.x)	xx.x (xx.x)	xx.x (xx.x)	xx.x (xx.x)	xx.x (xx.x)	ANOVA
Maternal height, cm (mean, SD, N)	xx.x (xx.x)	xx.x (xx.x)	xx.x (xx.x)	xx.x (xx.x)	xx.x (xx.x)	xx.x (xx.x)	ANOVA
Maternal Weight ,kg (mean, SD, N)	xx.x (xx.x)	XX.X (XX.X)	xx.x (xx.x)	xx.x (xx.x)	xx.x (xx.x)	xx.x (xx.x)	ANOVA
Maternal BMI (mean, SD, N)	xx.x (xx.x)	XX.X (XX.X)	xx.x (xx.x)	xx.x (xx.x)	XX.X (XX.X)	xx.x (xx.x)	ANOVA
Maternal MUAC, cm (mean, SD, N)	xx.x (xx.x)	xx.x (xx.x)	xx.x (xx.x)	xx.x (xx.x)	xx.x (xx.x)	xx.x (xx.x)	ANOVA
Maternal education, years (mean, SD, N)	xx.x (xx.x)	xx.x (xx.x)	xx.x (xx.x)	xx.x (xx.x)	xx.x (xx.x)	xx.x (xx.x)	ANOVA
Paternal age, years (mean, SD, N)	xx.x (xx.x)	xx.x (xx.x)	xx.x (xx.x)	xx.x (xx.x)	xx.x (xx.x)	xx.x (xx.x)	ANOVA
Paternal education, years (mean, SD, N)	xx.x (xx.x)	xx.x (xx.x)	xx.x (xx.x)	xx.x (xx.x)	xx.x (xx.x)	xx.x (xx.x)	ANOVA
Total number of persons in the household (mean, SD, N)	xx.x (xx.x)	xx.x (xx.x)	xx.x (xx.x)	xx.x (xx.x)	xx.x (xx.x)	xx.x (xx.x)	Kruskal-Wallis test
Total number of children below 5 years of age in the household (mean, SD, N)	xx.x (xx.x)	xx.x (xx.x)	xx.x (xx.x)	xx.x (xx.x)	xx.x (xx.x)	xx.x (xx.x)	Kruskal-Wallis test
Proportion with malaria parasiteamia at enrolment, number (percentage)	xxx / xxx (xx%)	xxx / xxx (xx%)	xxx / xxx (xx%)	xxx / xxx (xx%)	xxx / xxx (xx%)	xxx / xxx (xx%)	Chi-squared

Variable	Control	10g milk LNS	20g milk LNS	20g milk-free LNS	40g milk LNS	40g milk-free LNS
Mean (SD) change in length-for-age z-score mean, Z-score units	x.xx (x.xx)	x.xx (x.xx)	x.xx (x.xx)	x.xx (x.xx)	x.xx (x.xx)	x.xx (x.xx)
Raw p-value for intervention compared to control		x.xxx	x.xxx	x.xxx	x.xxx	X.XXX
Difference (95% CI) in means between the indicated intervention and the control group		xxx (xx to xx)	xxx (xx to xx)	xxx (xx to xx)	xxx (xx to xx)	xxx (xx to xx)
Mean (SD) change in length, cm	x.xx (x.xx)	x.xx (x.xx)	x.xx (x.xx)	x.xx (x.xx)	x.xx (x.xx)	x.xx (x.xx)
Raw p-value for intervention compared to control		X.XXX	X.XXX	X.XXX	X.XXX	X.XXX
Difference (95% CI) in means between the indicated intervention and the control group		xxx (xx to xx)	xxx (xx to xx)	xxx (xx to xx)	xxx (xx to xx)	xxx (xx to xx)

Table 2 Anthro	pometric	outcome	changes	during	and	up to	12 months	of intervention
						-		

		Model:		Model:				
	$\hat{\boldsymbol{y}}_i = \boldsymbol{b}_0 + \boldsymbol{b}_1 \boldsymbol{D}_i + \boldsymbol{b}_2 \boldsymbol{S}_i$			$\hat{y}_{i} = b_{0} + b_{1}D_{i} + b_{2}S_{i} + b_{3}(D_{i} \times S_{i})$				
Variable	Coefficient	90 % CI	P-value	Coefficient	90 % CI	P-value		
Constant (b ₀)	XX.XX	xx.xx to xx.xx	X.XXX	XX.XX	xx.xx to xx.xx	X.XXX		
Difference in mean change in LAZ in 40g dose LNS compared to 20g dose LNS (b ₁)	XX.XX	xx.xx to xx.xx	X.XXX	XX.XX	xx.xx to xx.xx	X.XXX		
Difference in mean change in LAZ in milk-free LNS compared to milk- containing LNS in 20 g group (b ₂)	XX.XX	xx.xx to xx.xx	X.XXX	XX.XX	xx.xx to xx.xx	X.XXX		
Difference in mean change in LAZ in milk-free LNS compared to milk- containing LNS in 40 g group $(b_2 + b_3)$				XX.XX	xx.xx to xx.xx	X.XXX		

Table 3 Regression results of the effects by the milk-containing and milk-free LNS

Table 4 Incidence of SAEs by study group

	Intervention group						
Intervention group	Control	10g milk LNS	20g milk LNS	20g milk- free LNS	40g milk LNS	40g milk- free LNS	P-value
Number of participants	XXX	XXX	XXX	XXX	XXX	XXX	
Number of participants with at least one episode of SAE (% with SAE)	xx (xx.x%)	xx (xx.x%)	xx (xx.x%)	xx (xx.x%)	xx (xx.x%)	xx (xx.x%)	XX.XXX
Raw p-value for intervention compared to control		X.XXX	X.XXX	X.XXX	X.XXX	X.XXX	
Risk ratio (95% CI) between the indicated intervention and the control group	1.00 (ref)	x.xx (xx to xx)	x.xx (xx to xx)	x.xx (xx to xx)	x.xx (xx to xx)	x.xx (xx to xx)	
Number of participants with fatal event (% with SAE)	xx (xx.x%)	xx (xx.x%)	xx (xx.x%)	xx (xx.x%)	xx (xx.x%)	xx (xx.x%)	XX.XXX
Raw p-value for intervention compared to control		X.XXX	X.XXX	X.XXX	X.XXX	X.XXX	
Risk ratio (95% CI) between the indicated intervention and the control group	1.00 (ref)	x.xx (xx to xx)	x.xx (xx to xx)	x.xx (xx to xx)	x.xx (xx to xx)	x.xx (xx to xx)	
Number of participants with life threatening event (% with SAE)	xx (xx.x%)	xx (xx.x%)	xx (xx.x%)	xx (xx.x%)	xx (xx.x%)	xx (xx.x%)	XX.XXX
Raw p-value for intervention compared to control		X.XXX	X.XXX	X.XXX	X.XXX	X.XXX	

Risk ratio (95% CI) between the indicated intervention and the control group	1.00 (ref)	x.xx (xx to xx)					
Number of participants with hospitalization (% with SAE)	xx (xx.x%)	xx (xx.x%)	xx (xx.x%)	xx (xx.x%)	xx (xx.x%)	xx (xx.x%)	XX.XXX
Raw p-value for intervention compared to control		X.XXX	X.XXX	X.XXX	X.XXX	X.XXX	
Risk ratio (95% CI) between the indicated intervention and the control group	1.00 (ref)	x.xx (xx to xx)					
Number of participants with significant disability (% with SAE)	xx (xx.x%)	xx (xx.x%)	xx (xx.x%)	xx (xx.x%)	xx (xx.x%)	xx (xx.x%)	XX.XXX
Raw p-value for intervention compared to control		X.XXX	X.XXX	X.XXX	X.XXX	X.XXX	
Risk ratio (95% CI) between the indicated intervention and the control group	1.00 (ref)	x.xx (xx to xx)					
Number of participants with other SAE (% with SAE)	xx (xx.x%)	xx (xx.x%)	xx (xx.x%)	xx (xx.x%)	xx (xx.x%)	xx (xx.x%)	XX.XXX
Raw p-value for intervention compared to control		X.XXX	X.XXX	X.XXX	X.XXX	x.xxx	
Risk ratio (95% CI) between the indicated intervention and the control group	1.00 (ref)	x.xx (xx to xx)					

Prevention of Linear Growth Faltering in Infants and Young Children With Lipid-based Nutrient Supplements (iLiNS-DOSE)

Statistical Analysis Plan

Appendix 01: Appendix 01: Secondary growth outcomes (added on 13.03.2013)

Contents

1.	Study objectives	3
2.	Hypotheses to be tested	3
3.	Definition of the secondary growth outcomes	3
4.	Basis for the analysis: Intention to treat and per protocol	4
5.	Time points for the analyses	4
6.	Presentation of the study findings and hypothesis testing	4
6 iı	1.1 Comparison of the anthropometric measurements at 18 months of age between ntervention groups versus the control group	4
6	.3 Incidence of various forms of undernutrition at a single time point	5
7.	General notes on statistical methods	5
7	.1 Software	5
7	.2 Preparing anthropometric data for analysis	5
7	.3 Multiple comparisons	5
7	.4 Confidence intervals	5
7	.5 Interaction and effect modification	5
7	.6 Covariate adjustment	5
8.	References	6
9.	Legends to the figures	6
10.	Figures	6
F	igure 1. Mean length-for-age z-score at 6, 12 and 18 months by intervention group	6
11.	Tables	7
Т	Cable 1 Comparison in anthropometric in the intervention groups at 18 months	7
Т	Cable 2 Anthropometric outcome changes during and up to 12 months of intervention	9
Т	Cable 3 Incidence of various forms of malnutrition at 18 months of age	12

1. Study objectives

The main aim of the trial was to assess the safety and impact of LNS supplementation on linear growth of infants and young children and to identify individual, household, and village-level characteristics that would modify the effects of LNS on child growth. A secondary aim is to similarly study the impact of LNS on various other (secondary) outcomes in the same target group.

The aim of these secondary analyses is to compare the following outcomes between infants in 6 different intervention groups: dietary supplementation with 10 g, 20 g or 40 g /day milk-containing LNS, 20 g or 40 g /day milk-free LNS or nothing (delayed intervention).

- 1. Change in weight-for-age (WAZ), weight-for-length (WHZ), mid-upper arm circumference (MUAC)-for-age and head circumference-for-age Z-scores
- 2. Incidence of stunting, underweight, and wasting

2. Hypotheses to be tested

- 1. Change in weight-for-age (WAZ), weight-for-length (WHZ), mid-upper arm circumference (MUAC)-for-age and head circumference-for-age Z-scores of infants provided with 10, 20, or 40 g/day of LNS from 6 to 18 months of age will be greater than that of infants who receive no dietary intervention at the same age.
- 2. Incidence of stunting, underweight, and wasting of infants provided with 10, 20, or 40 g/day of LNS from 6 to 18 months of age will be lower than that of infants who receive no dietary intervention at the same age.

3. Definition of the secondary growth outcomes

Change in weight-for-age (WAZ) and weight-for-length (WHZ) Z-scores rounded to two decimal points. Weight-for-age and weight-for-length at 6 (visit 0), 12 (Visit 26) and 18 months (visit 52) standardized by the WHO 2006 multi-centre growth standard. (*Form 00: Q2.5; Form 04: Q1.2, Q2.1, Q2.2, Q2.3, Q2.4*)

Change in length-for-age age Z-score (LAZ) rounded to two decimal points between 6 and 12 months of age (Figure 1). Length for age at 6 (visit 0) and 12 months (visit 26) standardized by the WHO 2006 multi-centre growth standard. (*Form 00: Q2.5; Form 04: Q1.2, Q2.2*)

Change in MUAC-for-age and head circumference-for-age Z-scores rounded to two decimal points at 6 (visit 0) and 18 months (visit 52) standardized by the WHO 2006 multi-centre growth standard. (*Form 00: Q2.5; Form 04: Q1.2, Q2.3, Q2.4*)

Incidence of stunting, underweight, and wasting. Moderate to severe stunting defined as LAZ <- 2.0 and severe stunting defined as LAZ <- 3.0 Z-score rounded to two decimal points. Incidence of stunting calculated at 12 and 18 months of age. Length for age at 12 months (visit 26) and 18 months (visit 52) standardized by the WHO 2006 multi-centre growth standard. (*Form 00: Q2.5; Form 04: Q1.2, Q2.2*)

Moderate to severe underweight defined as WAZ <-2.0 and severe underweight defined as WAZ <-3.0 Z-score rounded to two decimal points. Incidence of underweight calculated at 12 and 18 months of age. Weight for age at 12 months (visit 26) and18 months (visit 52) standardized by the WHO 2006 multi-centre growth standard. (*Form 00: Q2.5; Form 04: Q1.2, Q2.1*)

Moderate to severe wasting defined as WHZ <-2.0 and severe wasting defined as WHZ <-3.0 Zscore rounded to two decimal points. Incidence of wasting calculated at 12 and 18 months of age. Weight-for-length for age at 12 months (visit 26) and18 months (visit 52) standardized by the WHO 2006 multi-centre growth standard. (*Form 00: Q2.5; Form 04: Q1.2, Q2.1, Q2.2*)

4. Basis for the analysis: Intention to treat and per protocol

The basis for the analysis will be the same as that for the primary outcomes.

5. Time points for the analyses

All the above analyses will primarily cover the period from enrolment (when the participants are 6 months old) to the end of the intervention (when the participants are 18 months old).

6. Presentation of the study findings and hypothesis testing

6.1 Comparison of the anthropometric measurements at 18 months of age between intervention groups versus the control group

The group means and standard deviations for length (cm), weight (in kg), MUAC (cm), head circumference (cm) and LAZ, WAZ, WHZ, MUAC z-score and head circumference z-score (in z-score units) will be presented as indicated in Table 1. Group means and standard deviations for the change in anthropometric measurements and z-scores and their 95% confidence intervals between the control group and each of the intervention groups will be presented in Table 2.

Mean in anthropometrics, Z-score and change in measurements in each of the intervention groups will be individually compared against that of the control group using a two-sample t-test. The Holm's method will be used to adjust for the multiple comparisons (Aickin & Gensler,

1996). The raw P-values are presented in tables but the text and conclusion will be based on the Holm-adjusted P-values.

The null-hypothesis of LNS having no impact on linear growth is rejected for each comparison that yields a Holm's adjusted p-value <0.05.

6.3 Incidence of various forms of undernutrition at a single time point The analysis will compare proportions demonstrating various forms of undernutrition at age 18 months (Table 3). Global null hypotheses of no differences between groups and pair-wise comparisons will be tested by Fisher's exact test. Pair-wise comparisons of intervention to control will be done if global null hypothesis is rejected with P<0.05. Participants who had the condition initially will be excluded from the analysis of that form of undernutrition.

7. General notes on statistical methods

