- 2. To assess if LNS made without milk has a linear growth-promoting effect comparable to that of milk-containing LNS (in the above described environment, with 20 and 40 g/day ration sizes).
- 3. To determine the impact of five different LNS supplementation schemes on child dietary intake, morbidity, appetite, micronutrient status, immune function, and neuro-behavioral development.
- 4. To collect information to facilitate future demand creation for LNS interventions, such as end-user knowledge, attitudes and practices related to LNS and other feeding and parental care-giving practices.
- 5. To assess the extent to which household food insecurity and other individual, household, and village-level characteristics modify the effects of LNS on child outcomes.
- 6. To determine if any of the LNS supplements lead to increased risk of serious adverse events.

4 General approach to data analysis

There will be three categories of data analysis.

- 1. For the main aim (safety and linear growth outcomes), the analyses will be driven by predefined primary study hypotheses (see chapter 4 below). Conclusions on this part of the study will be based on formal hypothesis testing.
- 2. For the secondary aim (other outcomes), the analyses will be driven by similar hypotheses to those used for linear growth. These hypotheses have not been predefined in the trial protocol and hence they do not appear in version 1.0 of this SAP. They will, however, be defined as appendixes in subsequent versions of the SAP. For each hypothesis-driven analysis, the SAP will be updated prior to starting the analysis.
- 3. In addition to the hypothesis-driven questions, there will be a large number of exploratory analyses. In the absence of predefined study hypotheses, these analyses will be considered hypothesis-generating, rather than confirmatory.

5 Hypotheses to be tested

As indicated above, version 1.0 of the SAP describes predefined hypotheses only for the linear growth outcomes, i.e. specific objectives 1 and 2. Further hypotheses will be formulated and documented in subsequent SAP versions before the respective analyses are started.

- Objective 1 / hypothesis 1: The change in mean length-for-age Z-score (LAZ) of infants provided with 10, 20, or 40 g/day of LNS from 6 to 18 months of age will be greater than that of infants who receive no dietary intervention at the same age.

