11.2 Baseline information

Participant characteristics at enrollment will be tabulated by treatment arms as indicated in tables 1a and 1b. Hypothesis testing will be performed for baseline information to give additional information but p-values will not be presented in Table 1 of the eventual manuscript. Methods used for hypothesis testing are indicated in Tables 1a and 1b.

11.3 Comparison of the change in length-for-age Z-score between intervention groups versus the control group

Box-whisker plots of the change in LAZ of all 6 groups will be shown side by side in Figure 2. The group means and standard deviations for the change in length (in cm) and LAZ (in z-score units) will be presented as indicated in Table 2. The table will also tabulate the difference in mean length and LAZ and their 95% confidence intervals between the control group and each of the intervention groups.

Mean change in LAZ in each of the intervention groups will be individually compared against that of the control group using a two-sample t-test. The Holm's method will be used to adjust for the multiple comparisons (Aickin & Gensler, 1996). The raw P-values are presented in tables but the text and conclusion will be based on the Holm-adjusted P-values.

The null-hypothesis of LNS having no impact on linear growth is rejected for each comparison that yields a Holm's adjusted p-value <0.05.

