12.2 Preparing anthropometric data for analysis

All the anthropometric measurements were completed in triplicate during each study visit. But for the analysis, the team will use the mean of the first two readings if they do not differ more than by a pre-specified tolerance limit. If they do, the third measurement will be compared with the first and second measurements and the pair of measurements that has smaller difference will be used to calculate the mean which will be used in analyses. If there are only one or two repeated measurements mean of those two will be used for the analyses.

The agreed tolerance limits between the first two measurements are:

- 1. length/height ≤ 0.5 cm
- 2. circumferences (head, MUAC) ≤ 0.5 cm
- 3. infant/child weight ≤ 0.1 kg
- 4. adult weight ≤ 0.1 kg
- 5. skinfold thickness $\leq 2.0 \text{ mm}$

The length, circumference and skinfold thickness measurements were recorded to last complete unit (mm). To account for the bias of always rounding the values a bit downwards, half a unit will be added to all length, circumference and skinfold thickness measurements prior to the analysis. This procedure is not done for weight measurements, since they were recorded accurately with electronic scales.

Missing growth values will be treated as missing, i.e. there will be no growth data imputation from the other data. Imputation is considered unreliable due to long time-interval between anthropometric measurements, at an age when growth faltering is common.

When measuring change in anthropometric values between two time intervals, the change will be treated as missing if there is a missing value in either of the respective time points.

12.3 Multiple comparisons

The study involves multiple objectives and therefore multiple sets of hypothesis. Statistically, the different sets of hypotheses are considered independent families of hypotheses. Statistical adjustment for multiple comparisons in one family of hypotheses does not need to consider the other families.

For efficacy analysis, each family consists of 5 hypotheses, each comparing an intervention group versus the control group. The Holm's adjustment method is used.

For safety analysis, it is preferable to err on the cautious side (Nauta, 2010). We began with testing the global null hypothesis of no difference between groups. If the global null hypothesis is rejected, raw P-values are used in the comparisons between intervention and control groups.

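### Appendix 01, section 6.1 reuses the section 11.3 rejection sentence and so ties weight, arm and head circumference tests, and three further length measures, to the linear-growth null

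*SAP*

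**What the plan says.** The main SAP ties linear growth to one outcome. Hypothesis 1 in section 5 concerns "The change in mean length-for-age Z-score (LAZ) of infants provided with 10, 20, or 40 g/day of LNS" against no intervention, and section 7 names change in LAZ from 6 to 18 months as the primary growth outcome. Section 11.3 gives the test: "Mean change in LAZ in each of the intervention groups will be individually compared against that of the control group using a two-sample t-test". It then gives the decision rule, under which the null of "LNS having no impact on linear growth is rejected for each comparison that yields a Holm's adjusted p-value <0.05".

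Appendix 01 covers secondary growth outcomes. Its section 2 declares hypotheses on changes in WAZ, WHZ, MUAC-for-age and head circumference-for-age, and on the incidence of undernutrition. It declares none on mean length or mean LAZ. Section 6.1 then tests much more: "Mean in anthropometrics, Z-score and change in measurements in each of the intervention groups will be individually compared against that of the control group". The attained values at 18 months are in its Table 1 ("WHZ, MUAC z-score and head circumference z-score (in z-score units) will be presented as indicated in Table 1") and the changes in its Table 2 ("Group means and standard deviations for the change in anthropometric measurements and z-scores"). The paragraph that follows says conclusions rest on Holm-adjusted P-values and ends: "The null-hypothesis of LNS having no impact on linear growth is rejected for each comparison that yields a Holm's adjusted p-value <0.05".

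On multiplicity, section 12.3 sets efficacy families of five comparisons and adds: "Statistical adjustment for multiple comparisons in one family of hypotheses does not need to consider the other families". Appendix 01, section 7.3 adopts the same approach.

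**The concern.** The 11.3 sentence is right where it first appears, because the only tests before it are on change in LAZ. In 6.1 it follows tests on 18 measures and still names linear growth as the null. Three things follow.

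- A significant result on weight, MUAC or head circumference would, as written, reject a null about length.
- The mean z-score hypotheses that Appendix 01 does declare have no rejection rule naming them.
- Change in length, attained length and attained LAZ each test the same null as the primary analysis, each with its own 5% family, and nothing in 6.1 calls them supportive.

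Sections 11.3 and 6.1 can therefore answer one identically worded null in opposite ways, and no text says which governs. At stake is what may be reported as evidence of linear growth promotion.

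**Working it through.** **Counting the comparisons** (Appendix 01, Tables 1 and 2; five LNS arms against control):

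| Group of measures | Attained | Change | Measures | Comparisons (× 5) |
|---|---|---|---|---|
| Length-based: length, LAZ | 2 | 2 | 4 | 20 |
| Weight, MUAC, head circumference, WAZ, WHZ, MUAC z, head z | 7 | 7 | 14 | 70 |
| Total | 9 | 9 | 18 | 90 |

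One of the four length measures, change in LAZ, is the primary outcome itself, and for its 5 comparisons the sentence is correct. That leaves 90 − 5 = 85 comparisons outside the primary test: 70 on measures that are not length, and 15 on three further length measures.

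**The plan's own figure.** Six groups less the control give 5 comparisons per family, as section 12.3 states. Under a complete null, Holm rejects something in a family only if the smallest P-value is below 0.05 / 5 = 0.01, so the family-wise error is at most 5 × 0.01 = 0.05. With a shared control and equal arms (1932 / 6 = 322 per arm; equal allocation is an assumption), simulation gives 0.041 to 0.044. The 11.3 test is therefore controlled, and nothing in Appendix 01 alters it.

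**Linear-growth claim from any of the four length measures.** Four families treated as independent would give 1 − 0.95⁴ = 0.185, but that is not realistic. Section 7 computes LAZ from length, age and sex, so attained length and attained LAZ are near-duplicates, as are change in length and change in LAZ. The SAP gives no correlations, so these are assumptions: 0.90 to 0.98 within each pair and 0.3 to 0.7 between the pairs. Simulating six equal arms under no effect, with the first Holm step at 0.01 in each family, gives:

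- within 0.98, between 0.7: about 8.8%
- within 0.90, between 0.3: about 11.7%

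The chance that a further length measure rejects when change in LAZ does not is this figure less the primary family's own rate: 8.8% − 4.2% = 4.6%, up to 11.7% − 4.2% = 7.5%. That is the null risk of 6.1 contradicting 11.3 on length measures alone.

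**The 14 other measures.** A false-positive rate is the wrong yardstick here. If LNS truly changed weight but not length, the sentence would reject the linear-growth null correctly by its own terms and wrongly in substance, whatever the alpha. The error lies in the null that is named, and a multiplicity adjustment would not cure it.

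**The case against.** The strongest reply is that this is text carried over without changing the outcome name. Appendix 01 is titled as secondary, describes its analyses as secondary and declares its own hypotheses. Section 4 bases main-aim conclusions on the predefined primary hypotheses, and sections 5, 7 and 11.3 fix the primary outcome, test and rule. Change in length also already appears, with raw P-values, in the main SAP's Table 2. Leaving secondary families unadjusted against one another is an openly stated choice in section 12.3.

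Most of this stands, and it rules out three stronger readings that a reader might infer.

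- *That a secondary result can overturn the primary conclusion.* Nothing in the SAP says an Appendix 01 result replaces the one under 11.3. The two can contradict each other, and the text goes no further.
- *That the primary 5% error is lost.* The 11.3 family keeps its own control, at about 4%.
- *That the error is 38% (equal correlation 0.5) to 54% (independence) over all 18 measures, or 14% over the four length measures at equal correlation 0.5.* Equal or zero correlation is implausible for measures that pair up as raw value and z-score. The 18-measure figures also count any secondary result as proof of linear growth, which sections 5 and 7 do not do.

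The reply does not make the sentence correct. It is the only rejection rule stated for the comparisons of means in 6.1, and a probable copying slip in a decision rule is still a wrong rule.

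**Conclusion.** The point holds as an error in the stated decision rule of Appendix 01, section 6.1. For 70 of its 90 comparisons the rule names a null that the measure does not address. For 15 more it opens further routes to the linear-growth null without ranking them below change in LAZ. The primary analysis is intact. The 9% to 12% risk applies only if a linear-growth claim is accepted from any of the four length measures. It rests on equal arms, a complete null and the assumed correlations. The correction is worth making because section 6.1 bases its conclusions on these adjusted P-values.

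**What to change.** Replace the last sentence of the second paragraph of Appendix 01, section 6.1 with: *For each outcome, the null hypothesis of no LNS effect on that outcome is rejected for each comparison with Holm-adjusted P<0.05; these outcomes are secondary.*

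Add: *The conclusion on linear growth rests only on change in LAZ from 6 to 18 months (section 11.3); change in length, attained length and attained LAZ are supportive.*

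The Holm families of five and the approach in section 12.3 can stay as they are. The cost is SAP wording only, with no new data or analysis. The linear-growth conclusion then rests on one family, with error at most 5%, and the z-score hypotheses declared in the appendix gain a rule of their own.
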